6.4.1 Objective Response Rate (ORR)

Objective response rate is defined as the proportion of patients demonstrating an objective response during the study. Objective response includes complete responses (CR) and partial responses (PR) as defined in the RECIST 1.1 criteria and must be subsequently confirmed at least 4 weeks later.

[figure not shown]
6.4.2 Duration of Response (DOR)

Duration of response is measured from the time at which measurement criteria are first met for CR or PR (whichever status is recorded first) until the first date of progressive disease (PD) or death is objectively documented. Patient is censored at the last valid tumor assessment if PD or death has not been documented.

6.4.3 Progression Free Survival (PFS)

The PFS is defined as the time from the date of the first dose of the study drug to the earliest date of the first objective documentation of radiographic disease progression or death due to any cause according to Investigator assessment. Patients without documented PD or death, including those who dropped out, will be censored at their last tumor assessment. Patients who did not have any tumor assessments after the screening visit will be censored on the first dose date.

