6.9. Treatment Period

See the Schedule of Events for the timing of procedures during the Treatment Period ([Table 1](#)).

Please refer to the Pharmacy Manual for further information on treatment continuation after dose holds.

Physical and radiographic tumor assessments will be performed every 8 weeks (\pm 7 days) while the patient remains on the study drug and any other time during the study as clinically indicated. In accordance with RECIST v1.1, response (PR and CR) must be confirmed by a subsequent tumor assessment at least 4 weeks after the initial observed response. The same imaging modality used for baseline imaging (i.e., CT or MRI) must be used for subsequent radiographic tumor assessments. Any dose interruption after starting study treatment will not cause adjustment to the tumor assessment schedule. Additional tumor assessments may be performed as clinically indicated (e.g., if disease progression is suspected).

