2.3 Exploratory Objectives

3. STUDY DESIGN OVERVIEW

3.1 Overall Design

[figure not shown]
This is a Phase 2, multicenter, single-arm, open-label basket study designed to evaluate the safety and efficacy of milademetan in patients with advanced or metastatic solid tumors refractory or intolerant to standard-of-care therapy that exhibit wild-type (WT) tumor protein 53 (*TP53*) gene and *MDM2* copy number (CN) ≥ 8 using prespecified biomarker criteria.

Approximately 65 patients will be enrolled to receive milademetan.

Patients will receive the study drug until reaching disease progression (per Response Evaluation Criteria in Solid Tumors [RECIST] version [v]1.1), as determined by the Investigator; experiencing unmanageable toxicity; or until other treatment discontinuation criteria are met. Patients may be treated beyond tumor progression if they are experiencing clinical benefit based on the assessment of the Investigator in discussion with the Medical Monitor.

All patients will be followed for documentation of disease progression and survival information (i.e., date and cause of death). Long-term follow-up will continue every 8 weeks (± 7 days) until the endpoint of death, the patient is lost to follow-up, or for 24 months following the final dose of the study drug, whichever comes first.

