4.2 Secondary Endpoints

[figure not shown]
Secondary efficacy endpoints include:

- The DOR, defined as the time from the date of first response to the date of disease progression or death for patients with an objective response
- The PFS, defined as the time from the date of first dose to the earliest date of the first objective documentation of radiographic disease progression or death due to any cause
- The GMI will be determined using the ratio of time to progression (TTP) with n^{th} line of therapy (TTP_n ; here defined as milademetan) to the most recent prior line of therapy (TTP_{n-1})
- The DCR, defined as the percentage of patients who have achieved confirmed CR, PR, or stable disease (SD) for ≥ 16 weeks
- Overall survival, as measured from the date of the first dose of the study drug to the date of death due to any cause

Health-related quality-of-life endpoints include the QLQ-C30.

Safety endpoints include the incidence of TEAEs (including SAEs, TEAEs leading to dose reductions and TEAEs leading to discontinuation of study drug); changes in clinical laboratory parameters (hematology, serum or plasma chemistry), deaths, vital signs, and ECG parameters (especially QT intervals); physical examination results; and use of concomitant medications.

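### PFS is censored at the last tumor assessment but DOR at the last valid one; read literally, a non-evaluable final scan slightly lengthens PFS and can end the two endpoints on different dates

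*SAP*

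**What the plan says.** Both endpoints end at progression or death. In SAP 6.4.3 the PFS event is the "earliest date of the first objective documentation of radiographic disease progression or death due to any cause according to Investigator assessment". In SAP 6.4.2 DOR runs "until the first date of progressive disease (PD) or death is objectively documented". SAP 4.2 restricts DOR to responders: "the time from the date of first response to the date of disease progression or death for patients with an objective response".

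The rules for patients without an event differ by one word:

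- DOR (SAP 6.4.2): "Patient is censored at the last valid tumor assessment if PD or death has not been documented".
- PFS (SAP 6.4.3): "Patients without documented PD or death, including those who dropped out, will be censored at their last tumor assessment".
- PFS with no follow-up imaging (SAP 6.4.3): "Patients who did not have any tumor assessments after the screening visit will be censored on the first dose date".

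Neither PFS sentence carries the validity condition. The visible text does not define a valid assessment, and does not say how a non-evaluable scan is handled for either endpoint.

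**The concern.** A scan that cannot be evaluated does not show that the patient was free of progression on that date. If PFS is censored there, the patient stays in the risk set for one more interval during which progression could not have been seen. That lowers the estimated hazard, so the error can only go upward.

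The word *valid* in 6.4.2 must exclude some assessments or it does no work. A programmer who finds it in one section and not in the next could reasonably code two different dates, and two programmers could derive different PFS times from the same data. In a single-arm trial no control group shares the error. What is at stake is the reproducibility and slight optimism of a secondary endpoint. The primary endpoint is not involved.

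**Working it through.** **1. Who is affected.** The plan gives no figure to reproduce, so the first step is to compare the two rules case by case.

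| Patient | Effect of the missing word |
|---|---|
| Documented progression or death | None: both endpoints end on the event date |
| No event, last scan evaluable | None: both rules give the same date |
| No event, a non-evaluable scan followed by an evaluable one | None |
| No event, last scan non-evaluable, non-responder | PFS censored later; no DOR exists |
| No event, last scan non-evaluable, responder | PFS censored later than DOR |

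No event is created or removed. Only a censoring date moves.

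**2. Size per patient.** Protocol 6.9: "Physical and radiographic tumor assessments will be performed every 8 weeks", with a window of 7 days either side.

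- Between two successive scans: 56 days nominal, from 56 − 14 = 42 to 56 + 14 = 70.
- Only post-screening scan non-evaluable: PFS credited with about 56 days (56 ± 7 = 49 to 63) instead of being censored at first dose.
- Example responder: PR at day 56, last evaluable scan day 168, non-evaluable scan day 224, then lost. Literal PFS is censored at day 224. DOR is censored at day 168, giving 168 − 56 = 112 days. With one rule, both stop at day 168.

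**3. Size for 24-week PFS.** The documents give no expected PFS and no rate of non-evaluable scans. Assumptions: exponential PFS with a 16-week median; progression seen at the next 8-weekly scan; a share p of patients is assigned a non-evaluable last scan, falling at random on one of scans 1 to 6, independently of outcome.

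- True value: 0.5^(24/16) = 35.4%.
- Progression probability per interval: q = 1 − 0.5^(8/16) = 0.2929.
- Share of those at risk at scan i whose non-evaluable last scan is scan i: f_i = (p/6) / (1 − (i − 1)p/6).
- Valid-scan rule: these patients leave before scan i, the hazard stays at q, and the estimate stays at 35.4%.
- Literal rule: they stay in the denominator but their progression is not seen, so the hazard is q(1 − f_i), and S(24) is the product over i = 1 to 3 of 1 − q(1 − f_i).

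| p | f_1, f_2, f_3 | Literal S(24) | Excess, points |
|---|---|---|---|
| 5% | 0.0083, 0.0084, 0.0085 | 0.7095 × 0.7096 × 0.7096 = 35.7% | 0.4 |
| 10% | 0.0167, 0.0169, 0.0172 | 0.7120 × 0.7121 × 0.7122 = 36.1% | 0.8 |
| 15% | 0.0250, 0.0256, 0.0263 | 0.7144 × 0.7146 × 0.7148 = 36.5% | 1.1 |

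Some patients progress before their assigned scan. The share actually affected is p × (1 + 0.707 + 0.5 + 0.354 + 0.25 + 0.177)/6 = 0.498p, or about 2.5 to 7.5%. Of the planned number ("Approximately 65 patients will be enrolled to receive milademetan") that is roughly 2 to 5 patients.

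Simulated Kaplan-Meier curves with 65 patients agree: 0.4, 0.8 and 1.2 points. The valid-scan rule recovered about 35%, and the median changed in 5 to 8% of runs. The sampling standard deviation is about √(0.354 × 0.646/65) = 5.9 points.

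**4. A higher rate.** If instead 5 to 15% of patients still at risk left this way at every scan, f_i = p. The estimate is then (1 − 0.2929 × 0.95)³ = 37.6% to (1 − 0.2929 × 0.85)³ = 42.4%, an excess of about 2.2 to 7.0 points. This would remove about 0.05/(1 − 0.95 × 0.707) = 15% to 0.15/(1 − 0.85 × 0.707) = 38% of patients.

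**5. Size for the median.** A separate simulation used 65 patients, median PFS of 2 to 6 months and 10 to 30% early loss (all assumed). With a non-evaluable last scan in 10 to 25% of censored patients, the median shifted by 0.1 to 3.4 days on average and changed in at most 6% of runs. If every censored patient with a follow-up scan had one, the average shift was about 1 to 17 days, with a change in about 2 to 30% of runs.

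**The case against.** The strongest reply is that two rules are inferred, not stated. SAP 6.4.3 is silent on non-evaluable scans, and the missing word may be loose drafting. Relevant text is also out of sight: the general conventions in SAP 6.1 are partly redacted and the protocol's statistics section is not visible. This stands as far as intent goes. A reader might infer that the sponsor means non-evaluable scans to count for PFS; the documents do not say so.

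It does not remove the ambiguity. SAP 6.1 lets a specific section override the general conventions, and both specific sections are visible. A hidden definition of valid would not put the word into 6.4.3. Only a hidden rule that every tumor assessment means an evaluable one would settle the matter.

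A reader might also infer that PFS is biased in everyone who stops being assessed. That is too broad: if the last scan was evaluable, the two rules agree.

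A larger figure is tempting as well. One simulation of patients leaving after a non-evaluable scan gave excesses of 0.8 to 2.4 points. There, however, the valid-scan rule itself returned 35.9 to 38.6% against a true 35.4%. That error, up to 38.6 − 35.4 = 3.2 points, cannot come from the wording and points to departures related to outcome or to some other feature of the set-up. Nor does any visible text plan a 24-week PFS rate; SAP Section 8 lists only a PFS summary. The 24-week rate is used here as a yardstick.

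**Conclusion.** The inconsistency is real and minor. As written, SAP 6.4.3 permits PFS follow-up to be credited to a non-evaluable final scan while SAP 6.4.2 stops DOR earlier, and nothing visible resolves this. The error is in one direction, affects only patients without progression or death whose last scan is non-evaluable, and produces a PFS/DOR mismatch only in responders among them.

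Under independent non-evaluability in 5 to 15% of patients and a 16-week median, 24-week PFS is about 0.4 to 1.2 points too high, well inside sampling error, and the median usually stays where it is. A higher frequency, or departures related to outcome, would make it larger. The documents give no rate, so the range rests on assumption.

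ORR is untouched, and no visible test or decision depends on PFS. The finding does not extend to DCR: SAP 6.4.5 has no censoring rule, and no defect is shown there.

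**What to change.** In SAP 6.4.3, insert *valid* before *tumor assessment* in both censoring sentences, so that PFS stops at the last valid assessment and a patient with no valid assessment after screening is censored at first dose. Define valid once for PFS and DOR, for example as an overall time-point response other than not evaluable, unless the redacted text already does this. Leave DCR as it is.

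The change is to SAP wording only and should be made before database lock. It needs no new data. The downside is a PFS estimate that is slightly less favourable.

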6.4.5 Disease Control Rate (DCR)

The DCR is defined as the percentage of patients with confirmed CR, PR, or SD for at least 16 weeks (+/- 1 week window) according to RECIST v1.1 recorded in the period between the date of first study drug dose and disease progression or death due to any cause.

6.5 Safety Analysis

6.5.1 Overview of Safety Analysis Methods

All safety analysis will be performed for all patients in the Full Analysis Population. The following assessments will be used to evaluate the safety of milademetan:

[figure not shown]
- Adverse events (AEs)
- Medical history
- Vital sign measurements
- Physical examination findings
- Electrocardiogram (ECG)
- Liver Function Tests results (Hy's law)
- Eastern Cooperative Oncology Group (ECOG) performance status
- Laboratory assessments

6.5.2 Extent of Exposure

Extent of exposure to milademetan will be summarized by total dose, number of cycles, number of dose interruptions and number of dose reductions.

Dose intensity and relative dose intensity for milademetan will also be summarized.

Dose intensity will be calculated as the cumulative dose of the drug divided by total number of scheduled dosing days during the treatment.

6.5.1 Concomitant Medications

Concomitant medications will be defined as medications documented on the Concomitant Medications CRF and started on or after the C1D1. Concomitant medications will be coded using the World Health Organization (WHODrug) dictionary B3 Global March 2021 version and summarized in a table.

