5. SELECTION AND WITHDRAWAL OF PATIENTS

5.1. Inclusion Criteria

Each patient must meet all of the following criteria to be enrolled in the study:

[figure not shown]
1. Is \geq 18 years of age at the time of signing informed consent
2. Has signed and dated an informed consent form prior to the start of any study-specific qualification procedures
3. Has histologically and/or cytologically confirmed diagnosis of a cancer that is a locally advanced or metastatic solid tumor
4. Has measurable tumor lesion(s) in accordance with RECIST v1.1
5. Must have received all standard therapy appropriate for their tumor type and stage of disease or, in the opinion of the Investigator, would be unlikely to tolerate or derive clinically meaningful benefit from appropriate standard-of-care therapy

6. Has resolution of any clinically relevant toxic effects of prior chemotherapy, surgery, radiotherapy, or hormonal therapy

[figure not shown]

7. Presence of WT *TP53* and *MDM2* gene amplification by tumor tissue/blood testing, defined as:
 - a. ≥ 8 copies in tumor tissue by central laboratory or
 - b. ≥ 8 copies or 4-fold increase in tumor tissue or blood by local testing

8. Has an ECOG performance status of 0 or 1
9. Has adequate bone marrow function, defined as:
 - a. Platelet count $\geq 100 \times 10^9/L$
 - b. Hemoglobin $\geq 9.0 \text{ g/dL}$
 - c. Absolute neutrophil count $\geq 1.5 \times 10^9/L$
10. Has adequate renal function, defined as creatinine clearance $\geq 30 \text{ mL/min}$, as calculated using the modified Cockcroft-Gault equation (or equivalent glomerular filtration rate calculated using the Chronic Kidney Disease Epidemiology Collaboration formula)
11. Has adequate hepatic function, defined as:

- a. Alanine aminotransferase and aspartate aminotransferase $\leq 3 \times$ the ULN if no liver metastases are present or $\leq 5 \times$ ULN if liver metastases are present
- b. Total bilirubin $\leq 1.5 \times$ ULN or $\leq 3 \times$ ULN in the presence of liver metastases. Patients with Gilbert's disease who have serum bilirubin levels of $> 3 \times$ ULN may be enrolled
12. Is willing and able to comply with the protocol requirements
13. If requiring anticoagulation medication, should be on a stable regimen, defined as being on the same dose for at least 4 weeks

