6.8. Screening Period/Baseline Assessments

Patients may be screened at any time during the 21 days prior to the first dose of the study drug. Unless otherwise specified, Screening/baseline assessments may be done any time after consent and prior to the first dose of the study drug. Physical examination, ECOG, and clinical laboratory assessments on Cycle 1 Day 1 can be performed within 72 hours before the first dose of study drug. Patients who are determined not to meet eligibility criteria at any time prior to the first dose of the study drug will not be enrolled. The following will be assessed or measured at Screening/baseline:

- Informed consent

- Eligibility (including tumor assessment)
- Medical/disease history
- Smoking history: Smoking history should be documented on the eCRF page as “never,” “former” (with quit date), or “current” (document pack years)
- Demographics
- Physical examination focused on major organ systems that are clinically relevant as determined by the Investigator and including symptom directed findings and vital signs (taken 5 minutes after sitting), including height and weight
- ECOG Performance Status Scale
- ECG (12-lead) in triplicate
- Blood samples for laboratory assessments (see [Table 1](#)); ensure a serum pregnancy test is conducted for WOCBP
- Patient-reported outcomes: QLQ-C30
- Tissue as newly obtained biopsy or archived tissue \leq 5 years old for central diagnostic laboratory verification of WT *TP53* and *MDM2* CN. Tissue may be submitted as either:
 - FFPE block, or
 - at least 15 unstained, unbaked, positively charged slides with \geq 20% tumor tissue in 5-micron sections per slide as confirmed by a local pathologist

Note: Patients who have central testing of *TP53* and *MDM2* gene status performed under prescreening consent can forego this tissue submission requirement.

- In patients who provide consent to the optional procedure:
 - Tumor biopsy consisting of sufficient tissue to generate at least 15 slides of adequate quality
- Prior and concomitant medications:
 - Record all concomitant medication use after 21 days prior to Cycle 1 Day 1
 - Special attention should be accorded to medications that are known to cause prolongation of QTc or deplete potassium
- Baseline radiographic tumor assessment per RECIST v1.1:

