6.12. Concomitant Medications and Treatments

All concomitant medications (prescription and over-the-counter) and blood products taken from Screening until the EOT Visit will be recorded. The reason(s) for treatment, dose, and dates of treatment will be recorded. In addition, concomitant medications used to treat AEs occurring up to 30 days after the last dose of the study drug will be recorded.

See [Appendix A](#) for a list of prohibited medications and those medications that are permitted but should be used with caution during the study. Supportive care should be provided as appropriate to each patient to manage disease-related symptoms (e.g., antiemetics, antibiotics, transfusions, nutritional support, and pain control) according to institutional guidelines.

Use of filgrastim is allowed in accordance with ASCO/ESMO guidelines ([Klastersky 2016](#), [Smith 2015](#)).

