6.3 Demographic and Baseline Characteristics

Demographic data, medical history, concomitant disease, and concomitant medication will be summarized by means of descriptive statistics or frequency tables for the FAP.

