6.3.5 Prior and Concomitant Medications

Concomitant medications will be defined as medications documented on the Concomitant Medications CRF. Concomitant medications will be coded using the World Health Organization (WHODrug) dictionary B3 Global March 2021 and summarized in a frequency table.

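### The SAP defines concomitant medication in two conflicting ways, and the safety-section definition leaves out drugs begun before the first dose and continued on treatment

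*SAP*

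**What the plan says.** The SAP defines the term twice.

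- SAP 6.3.5, under baseline characteristics: "Concomitant medications will be defined as medications documented on the Concomitant Medications CRF". There is no date condition. The parent section, 6.3, says that "concomitant medication will be summarized by means of descriptive statistics or frequency tables for the FAP".
- SAP 6.5.1 (the second section with that number, under safety): "medications documented on the Concomitant Medications CRF and started on or after the C1D1". There is no clause for drugs begun earlier and still being taken. The safety overview places all safety analyses in the same Full Analysis Population.

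The safety endpoints in SAP 4.2 end with "physical examination results; and use of concomitant medications", and Protocol 4.2.2 names the same endpoint. The SAP's list of planned tables has a single concomitant-medication summary and does not say which definition it uses.

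The protocol collects medication by when it is taken. Under Protocol 6.12, prescription and over-the-counter drugs and blood products "taken from Screening until the EOT Visit will be recorded", with treatment dates. Drugs used to treat adverse events are recorded up to 30 days after the last dose. Protocol 6.8 has sites record use from 21 days before Cycle 1 Day 1 and adds: "Special attention should be accorded to medications that are known to cause prolongation of QTc or deplete potassium".

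**The concern.** A summary of concomitant medication should show what patients were taking while they were exposed to study drug. Under the 6.5.1 rule, a drug that a patient brought into the study and took in every cycle is not concomitant, because it started too early. Under the 6.3.5 rule, a drug stopped during Screening is concomitant, although it never overlapped study drug.

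This matters most for background drugs that bear on safety. The endpoint list singles out QT intervals among the ECG parameters, and Protocol 6.8 flags QTc-prolonging and potassium-depleting drugs at Screening. A reader of the safety results would want to know how many patients were on such drugs during treatment. A table built on 6.5.1 would show only those who began one after entry. The same planned table would also give different counts depending on which section the programmer followed.

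**Working it through.** No figure in the plan is at issue, so the check sets the rules side by side. Each pattern below is recorded under Protocol 6.8 or 6.12.

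| Pattern of use | Counted by SAP 6.3.5 | Counted by SAP 6.5.1 | Within the protocol's on-treatment or follow-up window |
|---|---|---|---|
| A. Begun and stopped before the first dose | Yes | No | No |
| B. Begun before the first dose, continued after it | Yes | No | Yes |
| C. Begun on or after the first dose, up to the EOT Visit | Yes | Yes | Yes |
| D. Begun after the EOT Visit to treat an adverse event, within 30 days of the last dose | Yes | Yes | Yes |

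Writing A to D for the numbers of medication records:

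- SAP 6.3.5 gives A + B + C + D.
- SAP 6.5.1 gives C + D.
- Use from first dose to the end of collection is B + C + D.

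So 6.5.1 undercounts by B, 6.3.5 overcounts by A, and the two differ by A + B. The population is the same in both sections, so the difference comes from the date rule alone.

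**Pattern B is not hypothetical.** Inclusion criterion 13 in Protocol 5.1 says that a patient who requires anticoagulation "should be on a stable regimen, defined as being on the same dose for at least 4 weeks". Protocol 6.1 treats a patient as enrolled at the first dose, and eligibility is settled before that. An anticoagulant that satisfies criterion 13 therefore began before Cycle 1 Day 1 and, if continued, falls in B. QTc-prolonging or potassium-depleting drugs found at Screening and continued fall in B as well.

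**Whether another output recovers B.** The planned prior-therapy tables cover anticancer medication, radiotherapy and surgery. The four planned listings cover serious adverse events, adverse events leading to discontinuation, deaths and potential Hy's Law cases. None would show a non-anticancer drug ongoing at entry. If the single table follows 6.5.1, B appears nowhere in the visible planned output.

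**Whether a precedence rule settles it.** SAP 6.1 lets specific sections override its general conventions. Both definitions sit in specific sections, so that sentence does not choose between them.

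**Size.** The documents give no rates of medication use at entry, so A and B cannot be estimated.

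**The case against.** The strongest reply is that nothing need be lost. Section 6.3.5 counts every drug on the CRF in the same population that is used for safety. The planned table comes after prior cancer therapy and before study medication, outside the safety block, which is roughly where 6.3.5 falls in the text. The safety overview's list of assessments does not include concomitant medication. The two sections could even be complementary: 6.3.5, whose heading covers prior drugs too, for everything recorded, and 6.5.1 for drugs newly started on treatment. A clarification may also sit in text that cannot be seen: Protocol 9.5 and SAP section 7 are not visible in the public version, and SAP 6.1 is partly blacked out.

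Much of this stands as a limit on the point. A reader might infer that the SAP removes all ongoing drugs from the endpoint. The documents do not support that, because the loss occurs only if 6.5.1 is the rule programmed. A reader might also infer that 6.5.1 targets the drugs that matter most for safety. It does not: it filters by start date, and it keeps a QT-active drug or an anticoagulant begun on study. Nor are CYP3A4-active drugs a good general example, since exclusion criterion 9 requires washout of strong inhibitors and of strong or moderate inducers. Finally, a frequency table does not link a drug to an individual patient's event. That takes patient-level records, which are collected in any case.

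What the reply does not remove is the conflict. Table order suggests which definition was meant but does not state it. The complementary reading is written nowhere in the visible text and would need two tables or a split table, where one is planned. If 6.3.5 is used, drugs stopped before the first dose are counted as concomitant.

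**Conclusion.** The point holds as a conflict between two stated definitions, neither of which matches use during treatment. Followed as written, the safety-section rule leaves continuing background drugs out of the summary of a named safety endpoint. The alternative rule adds drugs that never overlapped study drug.

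The consequence is limited to descriptive safety reporting. Objective response rate and the other efficacy analyses are unaffected, and no data are lost. It should be corrected, but it does not threaten the trial's main conclusions. No percentage of affected drugs can be given.

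Two assumptions apply. The first is that the start date used is the date the drug was first taken, not the date of a later dose-change entry. The second is that no text hidden from the public version already reconciles the definitions. If such text exists, the two visible definitions would still need to be aligned with it.

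**What to change.** Use one definition in SAP 6.3.5 and in SAP 6.5.1 (Concomitant Medications):

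- **Concomitant:** any medication taken on or after the first dose, whatever its start date and including drugs ongoing at Cycle 1 Day 1, through the end of the protocol's collection window. That window closes at the EOT Visit or, for drugs treating adverse events, 30 days after the last dose.
- **Prior:** any medication stopped before the first dose, reported separately.
- **Planned table:** state that the concomitant-medication summary uses this definition.

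The 30-day clause is needed because the EOT Visit is scheduled at 30 ± 7 days after the last dose, so it may fall at 30 − 7 = 23 days, or sooner if new anticancer therapy begins. A cut-off at the EOT Visit alone could miss adverse-event treatments that Protocol 6.12 records.

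The cost is a short SAP edit and a date-overlap rule in programming, made before database lock. The treatment dates are already collected. Handling of partial start or stop dates should be stated alongside it, unless the text not visible in the public version already covers it.
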